8.4 Immediately Reportable Events

8.4.1 Serious Adverse Events

Serious adverse events (SAEs) must be reported to the UFHCC Project Management Office ([contact]) within 24 hours of becoming aware of the event, and reported to the UF Health DISC within 5 days of being made aware of the event. All SAE's must also be reported to the IRB in accordance with the institution's policy per 21 CFR part 56.

The initial report must be as complete as possible, including details of the current illness and SAE and an assessment of the causal relationship between the event and study drug. Information not available at the time of the initial report (for example, an end date for the adverse event or laboratory values received after the report) must be documented and provided to DISC, PMO, and IRB in accordance with their reporting guidelines.

8.4.2 Other Events Requiring Immediate Reporting

Any overdose of treatment should be reported to the UF Health DISC within 5 days of being made aware of the event, and UFHCC Project Management Office ([contact]) within 24 hours of becoming aware of the event, regardless of association with a separate adverse event. In case the overdose did not result in any adverse event, the Investigator should report this as “overdose, no adverse event” and provide the intended amount, as well as the actual amount, of drug administered. In the event of overdose or exaggerated response, appropriate supportive measures should be employed. Actual treatment should depend on the severity of the clinical situation and the judgment and experience of the treating physician.

9. DISCONTINUATION

9.1 Discontinuation of Subjects

A subject must be discontinued from protocol-prescribed therapy under the circumstances defined in [Section 4.2](#).

If a female subject or the female partner of a male subject who is required to use defined contraceptive methods becomes pregnant after the study, the female subject or pregnant partner must be followed until the outcome of the pregnancy is known.

As far as possible, all end-of-study examinations must be performed on all subjects who receive the study drug but do not complete the study according to protocol. All subjects who discontinue from protocol-prescribed therapy for any of the reasons above will be followed for at least 28 days following the last day of study drug administration.

9.2 Replacement of Subjects

Subjects who are withdrawn prior to C1D1 for any reason will be replaced.

Phase Ib - Subjects who withdraw or are withdrawn from study prior to C1 Day 28 without a DLT will be replaced by another subject.

Phase II - Subjects who withdraw or are withdrawn prior to receiving one full cycle of therapy will be replaced by another subject.

9.3 Study Stopping Rules

During Phase Ib the study will be stopped if Dose Level -1 is not tolerated due to excessive toxicity.

During Phase II, the stopping rule for efficacy is inherently incorporated by using the Simon two stage design. For safety stopping rule, if 35% of the stage I study subjects (i.e., 5 subjects= 14 x 0.35) experience adverse events, the study will not proceed to the second stage of the study and will be terminated, regardless of efficacy result.

Also, as a Level 3 - high risk study as defined by DISC committee the study is subject to semi-annual review of the safety data. A decision may be made to allow additional subjects to be enrolled and treated after consultation with the DISC.

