7.2.3 Adverse Events

Adverse events that occur prior to dosing will be collected on Day 1 by questioning the subject regarding their occurrence since the screening visit. Adverse events will be collected at each

clinic visit based on observation and spontaneous reporting.

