8. ADVERSE EVENTS

8.1 Definitions

8.1.1 Adverse Event

The term “adverse event” includes any sign, symptom, syndrome, or illness that appears or worsens in a subject during the period of observation in the clinical study and that may impair the wellbeing of the subject. The term also covers laboratory findings or results of other diagnostic procedures that are considered to be clinically significant (*e.g.*, that require unscheduled diagnostic procedures or treatment measures, or result in withdrawal from the study).

The adverse event may be:

- A new illness/condition;
- Worsening of a sign or symptom of the condition under treatment, or of a concomitant illness/condition;
- An effect of the study drug; or
- A combination of 2 or more of these factors.

No causal relationship with the study drug or with the clinical study itself is implied by the use of the term “adverse event.”

Surgical procedures themselves are not adverse events; they are therapeutic measures for conditions that require surgery. The condition(s) for which the surgery is required may be an adverse event. Planned surgical measures permitted by the clinical study protocol and the condition(s) leading to these measures are not adverse events.

When a clear diagnosis is available that explains the abnormal objective findings, this diagnosis will be recorded as an adverse event and not the abnormal objective findings (*e.g.*, viral hepatitis will be recorded as the adverse event and not the transaminase elevation). If a definitive diagnosis is not available, then the sign(s) (*e.g.*, clinically significant elevation of transaminase levels) or symptom(s) (*e.g.*, abdominal pain) will be recorded as the adverse event.

Adverse events fall into the categories “serious” and “non-serious.”

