8.2 Period of Observation

For the purpose of this study, the period of observation for adverse events starts on the day the subject signs informed consent. For subjects who fail screening, the period of observation ends on the date of screening failure. Treated subjects, including those who were prematurely discontinued from the study, will be followed for any adverse events that occur during the study from the time the subject signs the informed consent form until 28 days (± 7 days) following the last dose of study treatment (i.e., the Follow-up Visit). However, if another course of anti-cancer therapy is initiated prior to the 28-day follow-up period visit, collection of adverse events will no longer be performed, with the exception of events that may be possibly, probably, or definitely related to the investigational agent or are clinically significant.

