8.3.2 Intensity of Adverse Events

The intensity of adverse changes in physical signs or symptoms will be graded according to the CTCAE version 4. For all other adverse events not described in the CTCAE, the intensity will be assessed by the Investigator using the following categories:

Mild (Grade 1) – transient or mild discomfort; no limitation in activity; no medical intervention/therapy required.

Moderate (Grade 2) – mild to moderate limitation in activity, some assistance may be needed; no or minimal medical intervention/therapy required.

Severe (Grade 3) – marked limitation in activity, some assistance usually required; medical intervention/therapy required, hospitalization is possible.

Life-threatening (Grade 4) – extreme limitation in activity, significant assistance required; significant medical intervention/therapy required, hospitalization or hospice care probable.

Death (Grade 5) – the event resulted in death.

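### The Phase II safety stopping rule does not define the adverse event it counts; read literally, it would probably end the trial after stage 1 at an assumed any-grade rate of 50%

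*Combined protocol and SAP*

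**What the plan says.** Section 9.3 (Study Stopping Rules) sets the Phase II safety rule to act "if 35% of the stage I study subjects (i.e., 5 subjects= 14 x 0.35) experience adverse events". The consequence is that "the study will not proceed to the second stage of the study and will be terminated, regardless of efficacy result". The next paragraph mentions semi-annual safety review and adds: "A decision may be made to allow additional subjects to be enrolled and treated after consultation with the DISC".

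The rule does not define its event, so the general definitions apply:

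- Section 8.1.1 covers any sign, symptom, syndrome or illness that appears or worsens and may impair wellbeing. It also covers "laboratory findings or results of other diagnostic procedures that are considered to be clinically significant". On causality it says: "No causal relationship with the study drug or with the clinical study itself is implied by the use of the term" adverse event.
- Section 8.3.2 starts its intensity scale for events outside the CTCAE at Grade 1, described as "transient or mild discomfort; no limitation in activity; no medical intervention/therapy required". Mild events are therefore adverse events.
- Section 8.2 says that "the period of observation for adverse events starts on the day the subject signs informed consent". Section 7.2.3 says: "Adverse events that occur prior to dosing will be collected on Day 1". Section 9.3 cites neither section.

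Elsewhere the protocol names a narrower class when it wants one. Section 2.2 refers to events of Grade 3 or higher, and Section 11.3.1 separates all, serious and treatment-related events. Section 3.3.2 lists the DLTs and requires relatedness.

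Section 11.1 gives the efficacy design: 14 evaluable subjects in stage 1, stop if 2 or fewer respond, 10 more otherwise, and reject a 20% CR rate if at least 8 of 24 respond.

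**The concern.** A mandatory termination rule needs a defined trigger, and this one has none beyond the broadest term in the protocol. Taken at its word, it counts mild and unrelated events equally with serious drug toxicity. In resistant AML treated with a cytotoxic drug, 5 of 14 subjects could easily have some such event.

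The primary Phase II question is answered only by the 8-of-24 test. If the literal rule usually stops the trial at 14 subjects, that test is usually never reached, even when the combination works as hoped. If the team instead applies a narrower event by custom, the choice is unwritten and may be made after the stage 1 data are seen. The protocol gives no operating characteristics for the safety rule under either reading.

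**Working it through.** **1. The plan's own figures.** The threshold is 14 x 0.35 = 4.9, rounded up to 5. Since 5/14 = 35.7% and 4/14 = 28.6%, 5 is the smallest count that reaches 35%.

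For the Simon design in Section 11.1, the rejection probability at response rate p is the sum over x = 3 to 14 of P(Bin(14, p) = x) x P(Bin(10, p) >= 8 - x). This gives 0.0874 at p = 0.20 and 0.8024 at p = 0.40. The stated type I error limit of 0.10 and power of 80% are both met.

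**2. Stop probability of the safety rule.** Let X be the number of the 14 stage 1 subjects with at least one qualifying event, X ~ Bin(14, q). The rule stops the trial if X >= 5. At q = 0.50:

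P(X <= 4) = (1 + 14 + 91 + 364 + 1001)/16384 = 1471/16384 = 0.0898, so P(X >= 5) = 0.910.

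The stop probability reaches 0.50 at q = 0.326 and 0.90 at q = 0.492.

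**3. Chance of a positive trial at a true 40% CR rate, with the safety rule in force.**

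- Under independence of responses and events: 0.8024 x P(X <= 4).
- With no assumption on dependence: from max(0, 0.8024 + P(X <= 4) - 1) to min(0.8024, P(X <= 4)).

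| Assumed event rate q | P(stop) | P(X <= 4) | Positive trial, independence | Bounds without independence |
|---|---|---|---|---|
| 10% | 0.009 | 0.991 | 0.795 | 0.793 to 0.802 |
| 20% | 0.130 | 0.870 | 0.698 | 0.672 to 0.802 |
| 25% | 0.258 | 0.742 | 0.595 | 0.544 to 0.742 |
| 30% | 0.416 | 0.584 | 0.469 | 0.387 to 0.584 |
| 40% | 0.721 | 0.279 | 0.224 | 0.082 to 0.279 |
| 50% | 0.910 | 0.090 | 0.072 | 0 to 0.090 |
| 60% | 0.982 | 0.018 | 0.014 | 0 to 0.018 |
| 2/3 | 0.996 | 0.004 | 0.003 | 0 to 0.004 |

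**4. Which rate applies.** The documents give no any-grade rate for this combination, so every q in the table is an assumption. The nearest figure is in Section 1.2: about two thirds of patients had grade 3/4 neutropenia on single-agent oral etoposide. That was 100 mg daily for 14 days in 21-day cycles, against 200 mg daily on Days 2 to 8 of 28 here. Under Section 8.1.1 a laboratory finding counts only if it is clinically significant. The figure is context and not an estimate, but it shows that 50% for all events of any grade is not extreme. It also shows that adding a grade alone, with haematologic events still counted, might leave the stop probability close to 1.

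**The case against.** The strongest reply is that nobody would apply the rule to mild or unrelated events. The Phase Ib rule in the same section refers to excessive toxicity, and 35% is close to the one-third DLT criterion, so a toxicity rule was probably meant. That is a fair inference, and for this reason 0.91 is a conditional figure and not a forecast. It does not supply the missing definition. Across narrower classes with rates of 10% to 30%, the same boundary stops the trial with probability anywhere from 0.009 to 0.42.

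A second reply is that the DISC may let more subjects enrol. That sentence follows the semi-annual review sentence in a separate paragraph and does not redefine the event. If it is an exception, it conflicts with the mandatory wording of the rule; if it is separate oversight, it gives no relief. The text does not say which, so the figures above hold only if it is not an exception.

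The denominator is a smaller matter. Section 9.3 prints 14 and Section 11.1 says 14 evaluable. Only the status of treated subjects who are replaced under Section 9.2 is open.

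A reader might infer three stronger points, which the documents do not support:

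- That the power statement is wrong. It is right for the Simon test, and the protocol never claims that it includes the safety rule.
- That pre-dose events certainly count. Sections 8.2 and 7.2.3 are general collection rules that Section 9.3 does not invoke; its window is simply unstated.
- That the DISC report in Section 10 must list every stage 1 subject with any adverse event as having met a stopping rule. The rule is met by a cohort, 5 of 14, and Section 10 does not say how that translates to individuals.

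**Conclusion.** The point stands: the event in a mandatory termination rule is undefined, and the only definition the protocol offers is the broadest one. It should be fixed before Phase II enrols. On the literal reading the rule would more likely than not end the trial after stage 1 once the per-subject rate passes about 33%, and would do so nine times in ten at about 49%. At 50% it leaves less than a 10% chance of a positive trial at a 40% CR rate, however responses and events are related.

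These sizes rest on three assumptions: the literal event class, an any-grade rate that the documents do not supply, and a DISC sentence that does not override the rule. The documents do not show that the trial will be stopped, or that the sponsor intends to count mild events. They do show that the event class decides whether the rule is workable, and that the class has not been chosen.

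**What to change.** Amend Section 9.3 so that one event class, chosen by the sponsor and the DISC, replaces the unqualified term. For example: *Stage 2 will not open if at least 5 of the 14 stage I subjects have [event class: grade, relatedness, and whether haematologic events count] between [start, stating consent or first dose] and [end].* In the same amendment:

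- State whether the DISC sentence is separate oversight or an exception to termination.
- Confirm whether treated stage 1 subjects replaced under Section 9.2 count.
- Report the stop probability of the 5-of-14 boundary over the range plausible for the chosen event, from the table above. Include the two-thirds row if haematologic events count.
- Report the chance of a positive trial at 40% CR beside it, labelled as assuming independence (0.795, 0.698, 0.595 and 0.469 at 10%, 20%, 25% and 30%).

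The cost is a short amendment to one section, with no extra patients or procedures. A narrower, rarer class raises the chance of a positive trial relative to the literal rule. The one downside is presentational: the reported joint power may be below the stated 80%, which follows from having any safety rule and not from the amendment.

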10. DATA AND SAFETY MONITORING

This protocol will be reviewed and monitored by the University of Florida Health Cancer Center (UFHCC) Data Integrity and Safety Committee (DISC). This study will have, at a minimum, semi-annual monitoring by the UFHCC DISC. Any adverse event fulfilling expedited reporting requirements must be reported to the DISC coordinator within 5 working days. The DISC coordinator will forward the report to the DISC Chairperson. Questions about subject safety or protocol performance will be addressed with the sponsor-investigator, statistician and study team members. Should any major concerns arise, DISC will offer recommendations regarding whether or not to suspend the trial.

UFHCC DISC data and safety monitoring activities include:

- Review of clinical trial conducted for progress and safety
- Review of all adverse events requiring expedited reporting as defined in the protocol
- Review of reports generated by data quality control review process
- Notification of the sponsor-investigator of recommended action
- Notification of sites coordinated by the UFHCC of adverse events requiring expedited reporting and subsequent committee recommendations for study modifications

In compliance with the UFHCC data and safety monitoring plan, the PI will provide a Data Integrity and Safety Committee Report to DISC at the predetermined timelines for the level of risk category assigned during the initial SRMC review.

UFHCC investigator-initiated protocols will be classified into one of the following categories of risk:

- Level 1 – Low risk non-therapeutic interventional trials.
- Level 2 – Moderate risk therapeutic (i.e., drug, biologic, or device) trials using FDA approved or commercially available compounds or interventions.
- Level 3 – High risk therapeutic trials (i.e., investigator-sponsored INDs, Phase I trials, studies requiring biosafety approval, or other areas that may be designated by NIH as high risk).
- Level 4 – Complex trials involving very high risk to subjects and a high level complexity (i.e., first in human or gene transfer studies).

The PI will summarize and provide DISC with all pertinent data related to the level of risk assigned by SRMC. This protocol summary will include a minimum of the following:

- The UF IRB assigned protocol number, UFHCC assigned protocol number, protocol title, PI name, data coordinator name or primary study coordinator, regulatory coordinator name, and statistician.
- Date of initial UF IRB approval, date of most recent consent UF IRB approval/revision, date of UF IRB expiration, study status, and phase of the study.
- Study target accrual and study actual accrual.
- Protocol objectives with supporting data and list of number of study participants who have met each objective.
- Measures of efficacy.
- Early stopping rules with supporting data and a list of the number of study participants who have met the early stopping rules.
- Summary of toxicities and protocol deviations.
- Summary of any recent literature which may affect the safety or ethics of the trial.

As part of the responsibilities assumed by conducting this study, the Principal Investigator (PI) agrees to maintain and have available for monitoring adequate case records (accurate source documents and CRFs) for the subjects treated under this protocol.

The PI will be primarily responsible for monitoring of adverse events, protocol violations, and other immediate protocol issues. The study coordinator will collect information on subjects enrolled through the use of electronic or paper adverse event (AE) forms, CRFs, and Informed Consent forms.

Identification of oversight responsibility:

The PI has primary responsibility.

The UFHCC DISC will meet at least semi-annually to review accrual, patterns and frequencies of all adverse events, protocol violations, and when applicable, internal audit results.

Description of internal (PI) safety review and monitoring process:

Adverse events will be reported along with all of the other collected data in the OnCore database. The PI or PI designee will report all adverse events to the UFHCC DISC and IRB per reporting guidelines.

11. STATISTICAL METHODS

The sections below provide an overview of the statistical considerations and analyses.

11.1 Determinations of Sample Size

An estimate of 8-24 patients are to be enrolled to Phase Ib portion of the study accounting for a 25% drop-out rate. Precise sample size cannot be defined, as it is dependent on the observed toxicity rate in this phase.

Subjects will be enrolled in the Phase II portion of the study once the MTD has been determined. The primary intention is to determine the complete response rate (CR + CR_i, see [Appendix A](#)) of ciprofloxacin and etoposide given at the MTD to subjects with resistant AML, which is achieved at the end of any treating cycle. The CR rate for AML subjects receiving etoposide alone is approximately 20% (the null hypothesis). We expect that the combination of ciprofloxacin and etoposide will improve the CR rate to 40%. In order to detect this difference with a type I error rate of 0.10 and power of 80%, when the true response rate is 40%, a minimum of 24 subjects who are evaluable for response will need to be accrued, based on the Simon's two-stage Minimax design. Specifically, in the first stage, we will enroll 14 evaluable subjects to this phase. The accrual will be temporarily suspended once the 14th evaluable subject is enrolled, pending response evaluation. If 2 or fewer respond, in these 14 subjects, the study will be stopped. Otherwise, continue to accrue additional 10 evaluable subjects (for a total of 24 evaluable subjects). The null hypothesis of 20% CR will be rejected if 8 or more CRs are observed in 24 subjects. Assuming 20% drop out rate, the total number of subjects to be enrolled to the Phase II portion is 30

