Safety Assessments:	
Subjects will be evaluated weekly during and for at least 28 days following the last cycle of chemotherapy. Assessments will include (See Table 1):
 
 • Interval history, review of systems, medications, new allergies, and physical examination with vital sign measurements; • Weekly laboratory assessments, including a CBC with differential and CMP; and • Toxicity assessment per the NIH Common Toxicity Criteria Adverse Event (CTCAE) version 4.
Efficacy Assessments:	
Efficacy parameters used to assess response include hemoglobin, ANC, platelet count, circulating blasts, and bone marrow aspirate and/or biopsy.

Sample Size Estimation	
In prior clinical trials of oral etoposide in resistant AML the CR rate has been approximately 20%. It is expect that the combination of etoposide with ciprofloxacin will improve CR to 40%. In order to detect this difference with type I error rate of 0.10 and power of 80%, when the true response rate is 40%, a minimum of 24 evaluable subjects will be treated in Phase II based on the Simon’s two-stage MiniMax design. Accounting for 15-20% drop out rate, a total of 30 subjects will need to be recruited to this phase.

Table 1. Study Events Schedule

Assessment	Screen (≤ 21 days prior to Day 1)	Cycle 1					Cycle 2		End of Treat- ment ¹² ± 7days	Long- Term Follow Up ¹³
		Day 1	Day 8±2	Day 15±2	Day 22±2	Day 28±2	Days 1, 8, 15, 22±2	Day 28±2		
Signed Informed Consent	X									
Demographics	X									
Medical /Treatment History	X									
Medication History ¹	X	X	X	X	X	X	X	X	X	
Interval History/Physical Examination	X	X	X	X	X	X	X	X	X	
Toxicity Assessment		X	X	X	X	X	X	X	X	
Review of Systems		X	X	X	X	X	X	X	X	
Weight	X	X	X	X	X	X	X	X	X	
ECOG Performance Status	X	X	X	X	X	X	X	X	X	
12-lead electrocardiogram (ECG) ²	X		X			X			X	
Vital Signs ³	X	X	X	X	X	X	X	X	X	
Hematology Laboratory Evaluations ⁴	X	X	X	X	X	X	X	X	X	
Blood Chemistry Laboratory Evaluations ⁵	X	X	X	X	X	X	X	X	X	
Serum Pregnancy Test (females) ⁶	X					X		X	X	
Administer Ciprofloxacin ⁷		X	X				X			
Administer Etoposide ⁸			X				X			
Bone Marrow Aspirate and/or Biopsy ⁹	X					X		X	X	
Adverse Events Assessments ¹¹	X	X	X	X	X	X ¹³	X	X	X	
Survival Assessment										X

¹ Document all medications taken during the two (2) weeks prior to screening and throughout and for 28 days after last treatment.

² Includes: rhythm, rate, and PR, QRS, and QTc intervals.

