3.3 Phase Ib

3.3.1 Dose Escalation and De-Escalation

The dose escalation phase of the study will utilize a standard “3+3” design to establish the MTD of oral ciprofloxacin in combination with a fixed dose of etoposide (200 mg daily on days 2-8). Ciprofloxacin will be given on days 1-10 at one of three dose levels shown in [Table 2](#). The MTD will be defined as the level associated with a < 1/3 chance of DLT. To summarize: (See [Figure 1](#))

- 1) Three subjects are initially treated at dose Level 0 (ciprofloxacin 750 mg twice daily).
 - a) If none of these experience DLT, then dose will be escalated to Level +1.
 - b) If one of these experiences DLT, then up to three more subjects are treated at Dose Level 1. If one or more of these develops DLT, then the MTD is considered to be exceeded and dose will be reduced to Level -1. If none of these additional subjects develop a DLT then the dose will be escalated to Level +1.
 - c) If 2/3 of these subjects experience DLT, then the MTD is considered to be exceeded and dose is reduced to Dose Level -1.
- 2) If the dose is escalated to Dose Level +1, the same process will be followed to determine if this is the MTD (no further escalation).
- 3) If the dose is reduced to Level -1, then the same process will be followed to determine if this is the MTD. If Dose Level -1 is above the MTD the study will be closed and it will be concluded that treatment with this combination at effective doses is not safe.

Table 2. Planned Dose Levels

Dose Level	Drug	Dose	Frequency	Schedule
0	Ciprofloxacin Etoposide	750mg 200mg	Twice Daily Once Daily	D1-10 D2-8
+1	Ciprofloxacin Etoposide	1000mg 200mg	Twice Daily Once Daily	D1-10 D2-8
-1	Ciprofloxacin Etoposide	500mg 200mg	Twice Daily Once Daily	D1-10 D2-8

[figure not shown]
Subjects withdrawn before Cycle 1 Day 1 (C1D1) will not be evaluable for dose escalation decisions and will be replaced in their treatment cohort. A subject is evaluable for dose-escalation decisions provided: they receive all drug doses and remain on study until evaluation at Cycle 1 Day 28 without a DLT; or they experience a DLT during Cycle 1. Subjects who miss any etoposide or ciprofloxacin doses or withdraw from study without a DLT and prior to Cycle 1, day 28 are not evaluable for dose escalation decisions and will be replaced in their cohort of treatment.

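### The stated 80% power for Phase II is that of the Simon efficacy rule alone; it leaves out the 5-of-14 safety stop in Section 9.3, whose counted event is not defined

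*Combined protocol and SAP*

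**What the plan says.** Section 11.1 sets the null CR rate at 20% and expects that the combination "will improve the CR rate to 40"%. It describes a Simon two-stage Minimax design and gives its error rates: "In order to detect this difference with a type I error rate of 0.10 and power of 80%, when the true response rate is 40"%. For stage I, "in the first stage, we will enroll 14 evaluable subjects to this phase". The trial stops if 2 or fewer of these 14 respond; otherwise 10 more are accrued, and the null is rejected at 8 or more responses in 24. The synopsis repeats the claim: "In order to detect this difference with type I error rate of 0.10 and power of 80%, when the true response rate is 40"%. Neither place mentions a safety stop.

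Section 9.3 treats the Simon design as the efficacy stop and then adds a safety stop. It sets the threshold at 35% of the stage I subjects, worked out as 5 of 14. If that many have adverse events, "the study will not proceed to the second stage of the study and will be terminated, regardless of efficacy result". The rule gives no grade, no relationship to study drug and no link to the DLT definition.

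Section 3.3.1 governs which dose reaches Phase II: "The MTD will be defined as the level associated with a < 1/3 chance of DLT". It gives no lower limit.

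**The concern.** To reject the 20% null, the trial must pass both stage I rules: at least 3 responses, and fewer than 5 subjects with a counted event. The printed power reflects only the first rule. Appendix D gives operating characteristics for the Phase Ib 3+3 rule, but nothing comparable exists for the Phase II safety stop, alone or combined with the efficacy rule.

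At stake is what the sponsor and the DISC believe about the trial's chance of a positive result. At a true CR rate of 40%, the efficacy rule stops at stage I with probability only 0.040. The safety stop can be much more likely than that, depending on an event the protocol does not define. The plan also does not say how a safety stop is to be reported against the efficacy hypothesis.

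**Working it through.** **Inputs.** From Section 11.1: p0 = 0.20, p1 = 0.40, n1 = 14, stop at 2 or fewer, n = 24, reject at 8 or more. From Section 9.3: stop at 5 or more of the 14 stage I subjects (14 × 0.35 = 4.9, taken as 5). From Section 3.3.1: an accepted DLT probability below 1/3.

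**Assumptions, not in the documents.** Each subject has a counted event with probability t, independently of response. The 14 subjects counted for safety are the 14 evaluable for response. The documents give no t, so a range is shown.

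**Step 1: reproduce the plan's figure.** For the efficacy rule alone,

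P(reject | p) = Σ over x = 3 to 14 of P(X1 = x | 14, p) × P(X2 ≥ 8 − x | 10, p).

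- At p = 0.40: power 0.802, with stage I futility stop 0.040.
- At p = 0.20: type I error 0.087, with stage I futility stop 0.448.

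A search over two-stage designs with type I error at most 0.10 and power at least 0.80 returns the same Minimax design (2/14, 7/24). Enrolment also agrees: 24 / (1 − 0.20) = 30. The stated figures hold for the rule they describe.

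**Step 2: add the safety stop.** Under independence,

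P(safety stop) = P(X ≥ 5 | 14, t)

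joint power = 0.802 × [1 − P(safety stop)]

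joint type I error = 0.087 × [1 − P(safety stop)]

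For example, at t = 0.20 the stop probability is 0.130, and 0.802 × (1 − 0.130) = 0.698.

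| Event rate t | P(safety stop) | Joint power (CR 40%) | Joint type I error (CR 20%) |
|---|---|---|---|
| 0.05 | 0.000 | 0.802 | 0.087 |
| 0.10 | 0.009 | 0.795 | 0.087 |
| 0.15 | 0.047 | 0.765 | 0.083 |
| 0.20 | 0.130 | 0.698 | 0.076 |
| 0.25 | 0.258 | 0.595 | 0.065 |
| 0.30 | 0.416 | 0.469 | 0.051 |
| 0.33 | 0.514 | 0.390 | 0.043 |
| 1/3 | 0.525 | 0.382 | 0.042 |
| 0.50 | 0.910 | 0.072 | 0.008 |
| 0.80 | 1.000 | 0.000 | 0.000 |

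(Products use unrounded values.)

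**Step 3: test the independence assumption.** Simulation with toxicity and response correlated within subject (Gaussian copula, ρ = −0.5 and +0.5) gives joint power of 0.69 to 0.71 at t = 0.20 and 0.36 to 0.42 at t = 0.33. The shift is at most about 0.03.

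**Step 4: see how far the undefined event matters.** If the event is DLT-type, which is an assumption, Section 3.3.1 accepts any rate below 1/3, and joint power runs from about 0.80 down to about 0.38. If any adverse event counts, the rate would be much higher. As an illustration only, Section 1.2 reports grade 3/4 neutropenia in about two thirds of patients in the cited oral etoposide trial, which used a different dose and schedule. At t = 2/3 the stop probability is 0.996, and joint power is 0.802 × (1 − 0.996), about 0.003.

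**The case against.** The strongest reply is that nothing printed is wrong. Section 11.1 ties the 80% to the Simon design in the same sentence, Section 9.3 labels the two stops separately, and quoting efficacy power without a separate safety stop is common practice. The first two statements are correct, so a reader who inferred an arithmetic error would be mistaken. What remains is that the safety stop as written is binding and overrides efficacy, and no combined figure is given.

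A reader might also infer that power is 0.39 to 0.70 at the toxicity rates the MTD definition accepts. The documents do not support that range. It needs a 20% floor that Section 3.3.1 does not contain; at accepted rates of 10% or less, power stays close to 0.80. Appendix D also shows that lower rates pass Phase Ib more readily: the chance of escalating is 0.91 at a true DLT rate of 10% and 0.43 at 33%. And Section 9.3 counts adverse events, not DLTs, so carrying the DLT limit into Phase II is itself an assumption.

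A third tempting inference is that the 5-of-14 stop contradicts the MTD definition. It does not: 4/14 = 28.6% is below 1/3 and 5/14 = 35.7% is above it, so 5 is the first count whose observed rate exceeds that limit. Stopping about half the time at a true rate near 1/3 is how a threshold placed there behaves.

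Finally, Section 9.3 ends by allowing additional subjects to be enrolled after consultation with the DISC. Its scope is unclear. If it permits the safety stop to be overridden, the loss of power would be smaller than shown, but the section does not say so.

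**Conclusion.** The 80% is a correct figure for the efficacy rule and an incomplete one for the Phase II design as written. The full design has about 80% power only if the counted event occurs in about 10% of subjects or fewer. Power is about 10 points lower at 20% (0.802 to 0.698) and about 41 points lower at 33% (0.802 to 0.390). On the literal any-adverse-event reading, little power remains. Type I error only falls, so the stated 0.10 limit is not threatened.

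These sizes rest on an assumed event rate, independence from response (relaxing it moves power by about 0.03 at most), the same 14 subjects being counted for both rules, and the safety stop being binding. The undefined event is the larger part of the problem, because it decides which row of the table applies. The finding is an omitted operating characteristic. It is neither a miscalculation nor a conflict with the MTD definition. It should be corrected.

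**What to change.** 1. The sponsor's statistician and the DISC state in Section 9.3 which event the 5-of-14 rule counts, and whether the closing sentence on DISC consultation can override the stop. The choice of event and threshold is theirs; none is proposed here.
2. In Section 11.1 and the synopsis, restate the power as about 80% (exact 0.802, type I error 0.087) for the efficacy rule alone, before the Section 9.3 safety stop.
3. Next to it, or in Section 9.3, give the stop probability, joint power and joint type I error over a range of rates plausible for the defined event, with the independence assumption stated.
4. State that a trial ended by the safety rule is reported as a toxicity stop, not as failure to reject the 20% null.

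The cost is wording in three places and one small table, with no added subjects. The downside is that the stated overall power becomes less favourable.
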